6.2 DETAILS OF TRIAL PROCEDURES AT SELECTED VISITS

6.2.1 Hospitalisation

Patients will be hospitalised for 3 – 4 days during cycle 1 as well as in the cycle when dose is escalated within one patient (single patient cohorts). In case that a step dosing approach is applied patient will also be hospitalised when dose is escalated to the normal dose (see [Section 5.2.1](#)). Patients will be hospitalised at start of cycle 2 for 24 hours and in all subsequent cycles for 8 hours in an outpatient setting.

6.2.2 Disease and Response Assessments for Multiple Myeloma

Clinical disease status for multiple myeloma will be assessed at screening, at the start of each cycle as well as at EOT.

At screening and subsequently the evaluation of multiple myeloma will be done according to IMWG (2006).

If a patient has clinical symptoms of multiple myeloma at screening, they should be recorded as baseline conditions.

Biomarkers in blood and urine will be done according to specific [Flow chart](#) for biomarkers.

Total body MRI should be performed within 14 days before day 1, cycle 1; results from routine assessments (MRI) for multiple myeloma are accepted if performed no later than 28 days before start of treatment.

Proprietary confidential information.

© 2018 Boehringer Ingelheim International GmbH or one or more of its affiliated companies. All rights reserved.

This document may not - in full or in part - be passed on, reproduced, published or otherwise used without prior written permission.

Total body MRI should be performed at or within 14 days before day 1, cycle 3; day 1, cycle 5; day 1, cycle 7 as well as every other cycle thereafter and at time of EOT.

Bone marrow aspirates will be done within 14 days before day 1 cycle 1 or at cycle 1, day 1 before start of treatment, when M protein/FLC becomes undetectable during treatment, at day 29 of cycle 3 and at EOT.

For karyotyping the recent analysis will be accepted if performed within 3 months prior to start of study medication in case that no therapy has been given between assessment of karyotyping and study medication; otherwise, a baseline karyotype should be performed at screening; subsequent karyotyping could be performed in subsequent marrow samples.

The biomarker assessments will be performed as specified in the [Flow charts](#). A bone marrow biopsy should be performed if aspirate could not be obtained (punctio sicca).

One sample of bone marrow will be provided for DNA banking in case that the patient has given consent for pharmacogenetic testing (baseline bone marrow, a bone marrow sample on treatment when a complete response is reached).

6.2.3 Screening and run-in period(s)

The examinations required for the screening visit may be conducted within a time interval of 21 days prior to the first study drug administration.

If for administrative or medical reasons, the patient is not entered within the defined screening period, it is allowed to re screen a patient. There is no maximum time period defined for re-screening.

If the patient has been determined eligible by the investigator to enter the trial (refer to [Section 3.3](#)), the investigator will assign one or more medication number(s) to the patient through the IWRS system at Visit 1 ([Section 4.1.2](#)). First dose of BI 836909 will be administered at the beginning of Visit 1 at the trial site (Day 1, cycle 1).

Proprietary confidential information.

© 2018 Boehringer Ingelheim International GmbH or one or more of its affiliated companies. All rights reserved.

This document may not - in full or in part - be passed on, reproduced, published or otherwise used without prior written permission.

Table 6.2.3: 1 Screening Visit (Day -21 to -1)

[figure not shown]
| | |
|--|--|
| Informed consent | Obtain written informed consent prior to enrolment in the trial and before any study-specific screening assessments are performed. Separate consent is required for none pre-specified pharmacogenetics and biomarker testing in bone marrow and blood. |
| Demographic data | Demographics and patient characteristics including detailed documentation of co-morbidities/concomitant diagnoses. Gender, date of birth/year of birth, race if allowed by local law will also be recorded. |
| Medical History | Oncological and relevant non-oncological baseline conditions will be recorded. |
| Physical examination (Section 5.2.6.2) | A general physical examination including blood pressure, heart rate and temperature as well as an orientated neurological examination will be performed, preferably by the same investigator throughout the study to enable comparability. |
| ECOG performance score (Section 5.2.6.2) | ECOG performance score will be assessed and documented. |
| Weight and Height (Section 5.2.6.2) | Height is measured at screening only. Weight is measured: preferably, the same weight scale should be used throughout the study to ensure consistency of data collected. |
| 12-lead ECG (Section 5.2.5) | Resting 12-lead ECG (digital) is performed and analysed locally. |
| Safety laboratory as well as screening for HCV, HBV and HIV (Section 5.2.4) | Haematology (including differential), biochemistry, coagulation parameters and urinalysis (dipstick), as well as screening for HCV, HBV and HIV |

Proprietary confidential information.

© 2018 Boehringer Ingelheim International GmbH or one or more of its affiliated companies. All rights reserved.

This document may not - in full or in part - be passed on, reproduced, published or otherwise used without prior written permission.

Table 6.2.3: 1 (cont'd) Screening Visit (Day -21 to -1)

| | |
|--|--|
| 
Bone marrow aspirate for disease assessment and DNA banking of bone marrow (Section 5.6.1)
 | 
Karyotyping: recent analysis will be accepted if performed within 3 months prior to start of study medication in case that no therapy has been given between assessment of karyotyping and study medication; otherwise, a baseline karyotype should be performed at screening; subsequent karyotyping could be performed in subsequent marrow samples.
 
The following assessments will be performed (see Flow charts):
 
 • MM cells in bone marrow; percentage (%) of plasma cells in bone marrow should be assessed locally according to institutional standards and documented in eCRF. • BCMA expression by myeloma cells in bone marrow 
Obtain bone marrow biopsy if aspirate could not be obtained (punctio sicca). One sample of bone marrow will be provided for DNA banking.
 |
| 
Disease assessment: Clinical/MRI and blood/urine (Section 5.6.1)
 | 
Evaluation of multiple myeloma according to IMWG (2006) Clinical: if patient has clinical symptoms of Multiple Myeloma, they should be recorded as baseline conditions.
 
Total body MRI should be performed; results from routine assessments (MRI) for multiple myeloma are accepted if performed no later than 28 days before start of treatment.
  |
| 
Adverse events (Section 5.2.2)
 | 
Occurrence of AEs since signing the Informed Consent Form will be documented. For patients who become screen failures, if an AE occurs during this period, the patient should be followed until the PI determines the patient is a screen failure.
 |

Proprietary confidential information.

© 2018 Boehringer Ingelheim International GmbH or one or more of its affiliated companies. All rights reserved.

This document may not - in full or in part - be passed on, reproduced, published or otherwise used without prior written permission.

Table 6.2.3: 1 (cont'd) Screening Visit (Day -21 to -1)

| | |
|---|--|
| Concomitant therapies (Section 4.2) | All concomitant therapies (including transfusions and anti-infectives) at trial entry and/or during screening will be recorded in the eCRF. |
| Review of inclusion/ exclusion criteria (Section 3.3.2 & 3.3.3) | Patient eligibility for the trial according to in- and exclusion criteria. In case of ineligibility, documentation of the reason(s) in patients source data why the patient is not eligible for the trial. |
| Serum pregnancy test (Section 5.2.4.1) | Serum pregnancy test in women of childbearing potential |

Proprietary confidential information.

© 2018 Boehringer Ingelheim International GmbH or one or more of its affiliated companies. All rights reserved.

This document may not - in full or in part - be passed on, reproduced, published or otherwise used without prior written permission.

6.2.4 Treatment period(s)

The first study drug dose should occur at the latest at Day 21 after the first screening procedure has been performed. A treatment cycle is defined as 6 weeks of duration. If initiation of a subsequent cycle is delayed due to medical reasons, additional visits beyond Day 36 may be necessary and may be performed at investigator's discretion, and should be recorded in the eCRF.

Patients may continue treatment in case of clinical benefit for 5 cycles. In case of ongoing clinical benefit up to a maximum of 5 additional treatment cycles can be given if considered indicated by the treating investigator.

6.2.4.1 Cycle 1

Patients will be hospitalized for the first 3 – 4 days.

Table 6.2.4.1: 1 Visit 1 (Day 1-3 or 4)

| | |
|---|--|
| Physical examination (Section 5.2.6.2) | A general physical examination will be performed, preferably by the same investigator through the study to enable comparability. This includes blood pressure, heart rate and temperature. Additional time points for blood pressure, heart rate and body temperature at the day of start of administration of BI 836909 are: prior to the start of premedication and infusion, then every 30 (± 10) minutes after start of the infusion of BI 836909 for the first 4 hours and additionally 3 times during hospitalisation (in the evening of day 1 as well as in the morning of day 2 and 3). Orienting neurological examination daily during hospitalisation. |
| Weight (Section 5.2.6.2) | Weight is measured; preferably, the same weight scale should be used throughout the study to ensure consistency of data collected. |
| PK samples (Section 5.5 and 5.2.5) | For PK sampling, see separate Flow chart as well as section 5.5 |
| Safety laboratory (Section 5.2.4) | Haematology, biochemistry, coagulation parameters and urinalysis (dipstick). |
| Adverse events (Section 5.2.2) | Occurrence of AEs since last visit. |
| Concomitant therapies (Section 4.2) | Any new or any change in concomitant therapies since the last visit, will be recorded in the eCRF. |

Proprietary confidential information.

© 2018 Boehringer Ingelheim International GmbH or one or more of its affiliated companies. All rights reserved.

This document may not - in full or in part - be passed on, reproduced, published or otherwise used without prior written permission.

Table 6.2.4.1: 1 (cont'd) Visit 1 (Day 1-3 or 4)

| | |
|---|---|
| 
Disease assessment: clinical and blood and urine markers (Section 5.6.1)
 | 
Clinical: if patient has any new clinical symptoms of multiple myeloma, these should be recorded in the “disease assessment” page and as an AE when applicable (see Section 5.2.2.1).
  |
| 
Administration of BI 836909 (Section 4.1)
 | 
4 weeks continuous intravenous infusion via infusion pump. Infusion bags must be exchanged approximately every 4 days.
 |
| 
Call IWRS/ Administer BI 836909
 | 
The IWRS system needs to be accessed (see Section 4.1.4) before any BI 836909 is administered to the patient. Dispense medication for the first course of treatment (see Section 4.1.4), as directed by the IWRS system.
 |

Proprietary confidential information.

© 2018 Boehringer Ingelheim International GmbH or one or more of its affiliated companies. All rights reserved.

This document may not - in full or in part - be passed on, reproduced, published or otherwise used without prior written permission.

Table 6.2.4.1: 2 Visit 2 – Visit 4 (Day 8 to day 22)

Home care service will be provided for bag exchange.

Assessments to be performed at start of each cycle:

| | |
|---|---|
| Body temperature, Blood pressure, heart rate (Section 5.2.6.2) | This examination includes blood pressure, heart rate and temperature. |
| Serum pregnancy test (Section 5.2.3) | Serum pregnancy test in women of childbearing potential |
| Safety laboratory (Section 5.2.4) | Haematology, biochemistry, coagulation parameters and urinalysis (dipstick). Immunoglobulins will be measured at visit 3 (day 15) |
| | |
| Adverse events (Section 5.2.2) | Occurrence of AEs since last visit. |
| Concomitant therapies (Section 4.2) | Any new or any change in concomitant therapies since the last visit, will be recorded in the eCRF. |
| Administration of BI 836909 (Section 4.1) | 4 weeks continuous intravenous infusion via infusion pump. Infusion bags must be exchanged approximately every 4 days |
| Call IWRS/ Administer BI 836909 | The IWRS system needs to be accessed (see Section 4.1.4.2) before any BI 836909 is administered to the patient. Dispense medication for the first course of treatment (see Section 4.1.4), as directed by the IRT system. |

Proprietary confidential information.

© 2018 Boehringer Ingelheim International GmbH or one or more of its affiliated companies. All rights reserved.

This document may not - in full or in part - be passed on, reproduced, published or otherwise used without prior written permission.

Table 6.2.4.1: 3 Visit 5 (Day 29 and day 30)

| | |
|---|--|
| Physical examination and [REDACTED] (Section 5.2.6.2) | A general physical examination will be performed, preferably by the same investigator through the study to enable comparability. This includes blood pressure, heart rate and temperature. [REDACTED] |
| PK samples (Section 5.5 and 5.2.5) | For PK sampling, see separate Flow chart and Section 5.6 . 
 • 10 minutes before the end of continuous infusion • 24 hours after stop of treatment (day 30) |
| Safety laboratory (Section 5.2.4) | Haematology, biochemistry, coagulation parameters and urinalysis (dipstick). |
| [REDACTED] | |
| Adverse events (Section 5.2.2) | Occurrence of AEs since last visit. |
| Concomitant therapies (Section 4.2) | Any new or any change in concomitant therapies since the last visit, will be recorded in the eCRF. |
| Body temperature, Blood pressure, heart rate (Section 5.2.6.2) | This examination includes blood pressure, heart rate and temperature. |
| Safety laboratory (Section 5.2.4) | Haematology, biochemistry, coagulation parameters and urinalysis (dipstick). |
| Adverse events (Section 5.2.2) | Occurrence of AEs since last visit. |
| Concomitant therapies (Section 4.2) | Any new or any change in concomitant therapies since the last visit, will be recorded in the eCRF. |

Proprietary confidential information.

© 2018 Boehringer Ingelheim International GmbH or one or more of its affiliated companies. All rights reserved.

This document may not - in full or in part - be passed on, reproduced, published or otherwise used without prior written permission.

6.2.4.2 Cycle 2 – 5 (or further cycles in case more than 5 cycles are administered)

Table 6.2.4.2: 1 Cycle 2 – 5 (or further cycles): Visit 1 (day 1)

Patient will be hospitalised for at least 24 hours.

| | |
|---|---|
| Physical examination (Section 5.2.6.2) | A general physical examination will be performed, preferably by the same investigator through the study to enable comparability. This includes blood pressure, heart rate and temperature. Orienting neurological examination daily during hospitalisation. |
| | |
| Weight (Section 5.2.6.2) | Weight is measured; preferably, the same weight scale should be used throughout the study to ensure consistency of data collected. |
| ECG/PK samples (Section 5.5 and 5.2.5) | For PK sampling, see separate Flow chart and Section 5.5 . A 12-lead ECG will be done at the start of each cycle. |
| Safety laboratory (Section 5.2.4) | Haematology, biochemistry, coagulation parameters and urinalysis (dipstick). |
| | |
| Adverse events (Section 5.2.2) | Occurrence of AEs since last visit. |
| Concomitant therapies (Section 4.2) | Any new or any change in concomitant therapies since the last visit, will be recorded in the eCRF. |

Proprietary confidential information.

© 2018 Boehringer Ingelheim International GmbH or one or more of its affiliated companies. All rights reserved.

This document may not - in full or in part - be passed on, reproduced, published or otherwise used without prior written permission.

Table 6.2.4.2: 1 (cont'd) Cycle 2 – 5 (or further cycles): Visit 1 (day 1)

[figure not shown]
| | |
|--|---|
| 
Disease assessment: Clinical, MRI and blood and urine markers (Section 5.6.1)
 | 
Clinical: if patient has any new clinical symptoms of multiple myeloma, these should be recorded in the “disease assessment” page and as an AE when applicable (see Section 5.2.2.1).
  
MRI should be performed every other cycle: at or within 14 days before cycle 3, day 1, cycle 5, day1, cycle 7, day 1... and/or at time of progression or start of further anticancer therapy;
 |
| 
Administration of BI 836909 (Section 4.1)
 | 
4 weeks continuous intravenous infusion via infusion pump. Infusion bags must be exchanged approximately every 4 days
 |
| 
Call IWRS/ Administer BI 836909
 | 
The IWRS system needs to be accessed (see Section 4.1.4.2) before any BI 836909 is administered to the patient. Dispense medication for the first course of treatment (see Section 4.1.4), as directed by the IRT system.
 |

Table 6.2.4.2: 2 Cycle 2 – 5 (or further cycles): Visit 2 - 4

| | |
|---|---|
| Physical examination (Section 5.2.6.2) | A general physical examination will be performed, preferably by the same investigator through the study to enable comparability. This includes blood pressure, heart rate and temperature. |
| | |
| Weight (Section 5.2.6.2) | Weight is measured; preferably, the same weight scale should be used throughout the study to ensure consistency of data collected. |
| ECG/PK samples (Section 5.5 and 5.2.5) | For PK sampling, see separate Flow chart and Section 5.5 . A 12-lead ECG will be done at the start of each cycle. |
| Safety laboratory (Section 5.2.4) | Haematology, biochemistry, coagulation parameters and urinalysis (dipstick). |
| Adverse events (Section 5.2.2) | Occurrence of AEs since last visit. |
| Concomitant therapies (Section 4.2) | Any new or any change in concomitant therapies since the last visit, will be recorded in the eCRF. |
| Disease assessment: clinical and blood and urine markers (Section 5.6.1) | Clinical: if patient has any new clinical symptoms of multiple myeloma, these should be recorded in the “disease assessment” page and as an AE when applicable (see Section 5.2.2.1) |
| | |

Proprietary confidential information.

© 2018 Boehringer Ingelheim International GmbH or one or more of its affiliated companies. All rights reserved.

This document may not - in full or in part - be passed on, reproduced, published or otherwise used without prior written permission.

Table 6.2.4.2: 2 (cont`d) Cycle 2 – 5 (or further cycles): Visit 2 - 4

| | |
|--|--|
| Bone Marrow | 
Bone marrow aspirate will be done on day 29 of cycle 3: The following assessments will be performed:
 
• MM cells in bone marrow; percentage (%) of plasma cells in bone marrow should be assessed locally according to institutional standards and documented in eCRF.• BCMA expression by myeloma cells in bone marrow• MRD (in case M protein/FLC becomes undetectable) 
Obtain bone marrow biopsy if aspirate could not be obtained (punctio sicca).
 
One sample of bone marrow will be provided for DNA banking.
 |
| Administration of BI 836909 (Section 4.1) | 
4 weeks continuous intravenous infusion via infusion pump. Infusion bags must be exchanged approximately every 4 days.
 |
| Call IWRS/ Administer BI 836909 | 
The IWRS system needs to be accessed (see Section 4.1.4.2) before any BI 836909 is administered to the patient. Dispense medication for the first course of treatment (see Section 4.1.4), as directed by the IWRS system.
 |

Proprietary confidential information.

© 2018 Boehringer Ingelheim International GmbH or one or more of its affiliated companies. All rights reserved.

This document may not - in full or in part - be passed on, reproduced, published or otherwise used without prior written permission.

Table 6.2.4.2: 3 Cycle 2 – 5 (or further cycles): Visit 6 (Day 36)

For all cycles except for last cycle

| | |
|---|--|
| Body temperature, Blood pressure, heart rate (Section 5.2.6.2) | This examination includes blood pressure, heart rate and temperature. |
| Safety laboratory (Section 5.2.4) | Haematology, biochemistry, coagulation parameters and urinalysis (dipstick). |
| Adverse events (Section 5.2.2) | Occurrence of AEs since last visit. |
| Concomitant therapies (Section 4.2) | Any new or any change in concomitant therapies since the last visit, will be recorded in the eCRF. |

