Please note: Death should always be reported as SAE in this trial unless due to underlying disease.
- 4 in case of clinical benefit a maximum of 5 cycles is administered. In case of ongoing clinical benefit up to a maximum of 5 additional treatment cycles can be given if considered indicated by the investigator ([Section 4.1.5](#)), visit 6 at day 36 must be performed for all cycles except the last one.
- 5 results from routine assessments (MRI) for multiple myeloma are accepted for screening if performed no later than 28 days before start of treatment ([Section 6.2.2](#))
- 6 ± 3 days
- 7 patients will be hospitalized in the first cycle for 3 or 4 days if first bag change will be performed in the clinic, on day 1 of cycle 2 for 24 hours, in patients within inpatient dose escalation at the time when dose is escalated also for 24 hours and in all subsequent cycles for 8 hours on day 1 of each cycle; patients will also be hospitalized at the end of cycle 1 (day 29); hospitalization may be prolonged in case a patient experiences a cytokine release syndrome or a severe AE ([Section 6.2.1](#)).
- 8 within 14 days before day 1 cycle 1 or on day 1 cycle 1 before start of treatment, when M protein/ Free kappa/lambda light chain (FLC) becomes undetectable during treatment, on day 29 of cycle 3 and at EOT
Karyotyping: recent analysis will be accepted for screening before start of treatment if performed within 3 months prior to start of study medication and in case that no therapy has been given between assessment of karyotyping and study medication; otherwise, a baseline karyotype should be performed at screening; subsequent karyotyping could also be performed in subsequent marrow samples (**tests to be done locally**).
Percentage (%) of plasma cells in bone marrow should be assessed locally according to institutional standards and documented in eCRF.
- 9 MRD (minimal residual disease assessment): when M protein/FLC becomes undetectable during treatment; day 29 of cycle 3 and EOT (tests to be done centrally).
- 10 Optional collection and bio-banking of a baseline bone marrow sample and a bone marrow sample on treatment when a complete response is reached.
- 11 at screening and at the beginning of each cycle (except for cycle 1).

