4.1.4.1.2 Monitoring for infusion-related reactions and cytokine release syndromes

Close monitoring of the patient during and after the infusion of BI 836909 is required for evaluation of infusion-related risks. The measures of monitoring include:

- Hospitalization of patients with access to intensive care days 1–4 of cycle 1 and in case of intra-patient dose escalation within the first cycle of dose escalation.
- Hospitalization of patients with access to intensive care on day 1 of cycle 2 (for a total of 24 hours) and in case of intra-patient dose escalation within the first cycle of dose escalation.
- Frequent measurements and documentation of blood pressure and heart rate (see [Section 5.2.6.1](#)).

In courses 2 and higher the patients are required to be hospitalized under close surveillance with access to intensive care days 1-3 again in case of infusion related events in earlier treatment courses. If no infusion related events occurred in earlier treatment courses an observation period of 4 - 8 hours in the hospital will suffice at start of each continuous infusion of BI 836909 in courses 3 and higher.

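### From cycle 3 onward the protocol gives incompatible in-hospital observation times at the start of infusion, and the days 1-3 rule after an earlier infusion-related event appears in only one section

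*Protocol*

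**What the plan says.** Four places in the current protocol text set the stay at the start of infusion in later cycles.

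- **Table 6.2.4.2:1 (visit table).** Its title is "Cycle 2 – 5 (or further cycles): Visit 1 (day 1"), so it covers cycle 2 and every later cycle. Directly beneath the title stands "Patient will be hospitalised for at least 24 hours", with no condition.
- **Section 6.2.1 (Hospitalisation).** "Patients will be hospitalised at start of cycle 2 for 24 hours and in all subsequent cycles for 8 hours in an outpatient setting". It sets no condition based on earlier reactions.
- **Flow chart, footnote 7.** "on day 1 of cycle 2 for 24 hours" and "in all subsequent cycles for 8 hours on day 1 of each cycle". The footnote lets the stay be prolonged if cytokine release syndrome (CRS) or a severe adverse event occurs. It has no rule based on what happened in earlier cycles.
- **Section 4.1.4.1.2 (monitoring for infusion-related reactions and CRS).** It gives 24 h on day 1 of cycle 2, then two branches. For patients with infusion-related events in an earlier course: "In courses 2 and higher the patients are required to be hospitalized under close surveillance with access to intensive care days 1-3 again". For patients without such events, in courses 3 and higher: "an observation period of 4 - 8 hours in the hospital will suffice".

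Sections 5.2.6.1 and 5.2.6.2 tie vital signs three times a day, continuous cardiac monitoring and a daily orienting neurological examination to the period of hospitalisation.

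**The concern.** A site that works from one of these places may be out of line with another. The main consequence is for a patient who restarts after an earlier reaction. Such patients are expected, because Section 4.1.4.1.4 allows the infusion to resume after a grade 1 or 2 infusion-related reaction and its table allows a restart after grade 2 CRS. For them Section 4.1.4.1.2 makes a longer stay mandatory, yet the flow chart, the section entitled Hospitalisation and the visit table do not mention it.

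Because part of the monitoring is attached to being in hospital, the length of stay determines how much of it the patient receives. CRS of grade 3 or higher and CNS events of grade 2 or higher are adverse events of special interest (Section 5.2.2.1). Events after cycle 1 that meet the DLT definition are considered when the MTD is confirmed and the recommended dose is chosen (Section 5.2.1). At stake are uniform patient protection and comparable intensity of observation across sites and cycles.

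**Working it through.** No formula applies, and the plan states no figure to reproduce. The check is a side-by-side reading by cycle and by patient history.

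| Source | Cycle 2, no earlier events | Cycle 2, earlier events | Cycle 3+, no earlier events | Cycle 3+, earlier events |
|---|---|---|---|---|
| Table 6.2.4.2:1 | at least 24 h | at least 24 h | at least 24 h | at least 24 h |
| Section 6.2.1 | 24 h | 24 h | 8 h | 8 h |
| Flow chart footnote 7 | 24 h | 24 h | 8 h | 8 h |
| Section 4.1.4.1.2 | 24 h | days 1-3 | 4-8 h | days 1-3 |

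Taking the columns in turn:

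1. **Cycle 2, no earlier events.** All four are compatible with 24 h. There is no conflict.
2. **Cycle 2, earlier events.** A stay on days 1-3 meets the visit table's minimum of 24 h, so those two can both be followed. Footnote 7 and Section 6.2.1 give 24 h and omit the longer requirement.
3. **Cycle 3 onward, no earlier events.** A stay of 8 h meets footnote 7, Section 6.2.1 and the upper end of 4-8 h, but not the visit table. The visit table's minimum is 24 / 8 = 3 times the 8 h stay and 24 / 4 = 6 times the shortest acceptable stay.
4. **Cycle 3 onward, earlier events.** The stated stay is 8 h, at least 24 h, or days 1-3. A stay of 8 h meets neither the visit table nor Section 4.1.4.1.2. The protocol does not express days 1-3 in hours, so no ratio is given.

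As to monitoring, Section 5.2.6.1 schedules vital signs every 30 minutes for 4 h after the start of infusion and then three times a day during hospitalisation. A 4 h stay can end when the 30-minute checks end; a stay of 24 h or more carries the hospital-based checks into day 2. Section 6.2.1 also describes the 8 h as hospitalisation "in all subsequent cycles for 8 hours in an outpatient setting", which leaves it unclear whether checks defined by hospitalisation apply at all during those hours.

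**The case against.** The strongest reply is that the conflict is narrower than a list of four durations suggests, and much of that reply stands.

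- A reader might infer four mutually contradictory rules. That is not so. The 4-8 h and days 1-3 statements are two branches of one section for different patients, and 8 h lies within 4-8 h. For patients without earlier events, the visit table alone is out of line.
- A reader might infer that cycle 2 is affected to the same degree. It is not: no place gives less than 24 h in cycle 2, and what remains there is an exception that is not carried across.
- A reader might infer that CRS or CNS events would be missed. The documents do not support that. Section 5.2.3 requires adverse events to be collected through the residual effect period whether or not the patient is in hospital. Section 5.2.6.1 also applies vital signs three times a day in case of CRS, and lets the investigator modify surveillance in later applications according to tolerability. Footnote 7 allows a longer stay for CRS or a severe event. An effect on event detection is possible but is not shown or quantified.
- The documents do not say which of these places sites consult at a visit, so no actual departure from Section 4.1.4.1.2 can be asserted.

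These points limit the consequence but do not remove the conflict. The visit table's title names cycles 2 to 5 and any further cycles, so its 24 h cannot be read as meant for cycle 2 alone. Footnote 7's prolongation is optional and is prompted by an event the patient experiences; it does not replace a mandatory rule that depends on earlier courses. Discretion over surveillance does not settle which minimum stay applies.

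**Conclusion.** The concern holds as an internal inconsistency in the protocol, mainly for cycle 3 onward. The stated stay there ranges from 4-8 h to at least 24 h for patients without earlier infusion-related events, and from 8 h to days 1-3 for patients with them. In cycle 2 the only defect is that the days 1-3 requirement stands in Section 4.1.4.1.2 alone.

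What follows is that the intensity of in-hospital surveillance depends on the section followed. It would go too far to conclude that the MTD is compromised: it is defined on DLTs in cycle 1 (Protocol Sections 5.2.1 and 7.3.1; SAP Section 7.4), and the stays at issue begin in cycle 2. Later-cycle events contribute only to confirming the MTD and choosing the recommended dose. No statistical figure changes.

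The conclusion rests on reading each statement at its stated scope. It makes no judgement on which duration is clinically right. The correction should be made, because it bears on patients re-exposed after a reaction.

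**What to change.** Reconcile Table 6.2.4.2:1, Section 6.2.1, flow chart footnote 7 and Section 4.1.4.1.2 into one statement set out by cycle (2; 3 and later) and by history of infusion-related events (none; any), and repeat it in the flow chart and the visit table. State whether the checks tied to hospitalisation in Sections 5.2.6.1 and 5.2.6.2 apply during a stay described as outpatient. The required duration in each case is for the sponsor's clinical team to decide. The cost is protocol wording only; no analysis or sample size changes.
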